#### 4.1.2 Selection of doses in the trial and dose modifications

##### 4.1.2.1 Treatment with BI 1358894

The following doses are selected for this trial:

[figure not shown]
5 mg, qd  
25 mg, qd  
75 mg, qd  
125 mg, qd

[figure not shown]
The criteria for selection are based on preclinical and clinical data of BI 1358894 gathered during research and development.

In general, dose range finding studies intend to test a broad range of exposures for dose finding using the MCPMod approach.

[REDACTED]

|  |   |   |   |   |   |   |   |   |  |
|--|---|---|---|---|---|---|---|---|--|
|  |   |   |   |   |   |   |   |   |  |
|  |   |   |   |   |   |   |   |   |  |
|    |   |   |   |   |   |   |   |   |  |
|     |    |    |    |    |    |    |    |    |    |
|     |    |    |    |    |    |    |    |    |    |
|     |    |    |    |    |    |    |    |    |    |
|     |    |    |    |    |    |    |    |    |    |
|  |   |   |   |   |   |   |   |   |  |
|   |  |  |  |  |  |  |  |  |  |
|   |  |  |  |  |  |  |  |  |  |
|   |  |  |  |  |  |  |  |  |  |
|   |  |  |  |  |  |  |  |  |  |

#### 4.1.2.2 Treatment arm with quetiapine

After up-titration from Day 1 until Day 4 from 50 mg to 150 mg quetiapine, once daily, the targeted daily treatment dose until end of treatment will be 300 mg, which is the recommended daily dose according to the SmPC for the augmentation therapy as standard of care for the indication MDD.

If a participant, in the medical judgment of the investigator, and assuming that the participant is assigned to the treatment arm with quetiapine, is not able to tolerate the evening dose, then there is a one-time option of reducing dosage from two tablets (equals to 300 mg quetiapine /Placebo) to one tablet (equals to 150 mg quetiapine or placebo) in the evening, on Week 1 (V3) visit.

Thereafter, this finally chosen dose must be stable until end of treatment at Week 6. Further adjustments of the assumed daily quetiapine dose are not allowed and will lead to an early discontinuation.

#### **4.1.4 Drug assignment and administration of doses for each participant**

The medication assignment will be provided through IRT. The assigned medication number(s) must be entered in the eCRF, and the corresponding medication kit(s) must be given to the participant. The duration of treatment is 6 weeks. The last dose of trial medication should be taken on the day before the EOT Visit.

At Visit 2, after randomization, participants will receive medication kits for the double-blind treatment period. The morning dose of trial medication will be taken at the trial site under supervision of the investigator or site staff. Participants will bring trial medication (used/unused blister and covering packages) to site visits for compliance check (V3/V4/V6/V8). At visits V2, V4 and V6, participants will return used/unused medication kits and receive new supplies for a total of 14 treatment days (14 treatment days plus 3 days reserve) for BI 1358894 and quetiapine.

Participants should be instructed not to take their trial medication in the morning of Visit 4 and Visit 6, as participants will be dosed at the site [REDACTED]. Participants should also be instructed not to take their trial medication in the morning of Visit 8/EOT/eEOT Visit, as a [REDACTED] at that visit. For participants who complete the treatment period, the last dose of trial medication should be taken on the day before the EOT Visit. Participants who fail to do so should have the visit rescheduled as soon as possible, ideally on the following day.

Participants should be instructed to take the BI 1358894 tablets or matching placebos orally with water and in a consistent way, i.e., either with or without food every morning at approximately the same time. If a morning dose is missed by more than 12 hours, that dose should be skipped and the next dose should be taken as scheduled. On days prior to a visit, the morning dose should be taken approximately 24 hours before the planned morning dose at the clinic visit. A dose reduction of BI 1358894 is not possible.

Table 4.1.4: 1 Dosage and Treatment Schedule for BI 1358894 / Matching Placebo

|            | 5mg tablet   | 25mg tablet | 50mg tablet | PBO matching 5mg tablet | PBO matching 25mg tablet | PBO matching 50mg tablet |
|------------|--|-------------|-------------|-------------------------|--------------------------|--------------------------|
| Dose group | Number of tablets to be taken daily – in the morning ☺ |             |             |                         |                          |                          |
| PBO        | 0  | 0           | 0           | 1                       | 1                        | 2                        |
| 5 mg       | 1  | 0           | 0           | 0                       | 1                        | 2                        |
| 25 mg      | 0  | 1           | 0           | 1                       | 0                        | 2                        |
| 75 mg      | 0  | 1           | 1           | 1                       | 0                        | 1                        |
| 125 mg     | 0  | 1           | 2           | 1                       | 0                        | 0                        |

Quetiapine or matching placebo should be taken prior to bedtime. The daily active dose at the start of therapy is 50 mg on Day 1, 100 mg at Day 2 and 150 mg on Day 3 and 4. Beginning with Day 5, the recommended daily dose of 300 mg will be taken. If an evening dose is missed before midnight, that dose should be skipped and the next dose should be taken the next evening. On days prior to a visit, the evening dose should be taken at least 8 hours before the planned dose at the visit.

Table 4.1.4: 2 Dosage and Treatment Schedule for Quetiapine / Matching Placebo Titration and Maintenance Phase

|            | 50 mg tablets or matching placebo                      | 150 mg tablets or matching placebo |
|------------|--|------------------------------------|
| Trial Day  | Number of tablets to be taken daily – in the evening ☺ |                                    |
| Day 1      | 1  | 0                                  |
| Day 2      | 2  | 0                                  |
| Day 3      | 0  | 1                                  |
| Day 4      | 0  | 1                                  |
| Day 5 - 43 | 0  | 2                                  |

The need to decrease the dose from 300 to 150 mg/day should be based on individual participant evaluation. In this case, the PI will instruct the participant to only take one tablet of the evening dose instead of two. This dose reduction is a one-time option at Visit 3 after the first week of treatment.

During the COVID-19 pandemic, there might be situations that would not allow a participant to come to the site for the study visit. If the investigator judges it as acceptable and safe to continue trial medication, trial medication might be shipped from the site to the participant (for more details see section [6.1](#) and [10.4](#)).

#### 4.1.5 Blinding and procedures for unblinding

##### 4.1.5.1 Blinding

At each treatment day, all participants will take the trial medication in the morning and in the evening to ensure the blinding of their treatment arm. Participants, investigators, central reviewers, and everyone involved in trial conduct or analysis or with any other interest in this double-blind trial will remain blinded with regard to the randomized treatment assignments until the time specified in the database lock process, with the exceptions described in this section below.

The access to the randomisation code will be kept restricted until its release for analysis.

The randomisation codes will be provided to bioanalytics prior to last participant completed

[REDACTED] Bioanalytics will not disclose the randomisation code or the results of their measurements until the trial is officially unblinded.

Dedicated database snapshots (no partial DBL) will be generated prior to DBL to allow for development and refinement of

[REDACTED]

No formal interim report will be generated. Final [REDACTED] will be reported once after availability of data from DBL.

##### 4.1.5.2 Unblinding and breaking the code

Emergency unblinding will be available to the investigator via IRT. It must only be used in an emergency situation when the identity of the trial drug must be known to the investigator in order to provide appropriate medical treatment or otherwise assure safety of trial participants. The reason for unblinding must be documented in the source documents and/or appropriate CRF page.

Due to the requirements to report Suspected Unexpected Serious Adverse Reactions (SUSARs), it may be necessary for a representative from BI's Pharmacovigilance group to access the randomisation code for individual participants during trial conduct. The access to the code will only be given to authorised Pharmacovigilance representatives for processing in the PV database system and not be shared further.

#### 4.1.6 Packaging, labelling, and re-supply

The investigational medicinal products will be provided by BI or a designated CRO. They will be packaged and labelled in accordance with the principles of Good Manufacturing

Practice (GMP). Re-supply to the sites will be managed via an IRT system, which will also monitor expiry dates of supplies available at the sites.

For details of packaging and the description of the label, refer to the ISF.

#### **4.1.7 Storage conditions**

Drug supplies will be kept in their original packaging and in a secure limited access storage area according to the recommended storage conditions on the medication label. A temperature log must be maintained for documentation.

If the storage conditions are found to be outside the specified range, the Clinical Research Associate CRA (as provided in the list of contacts) must be contacted immediately.

#### **4.1.8 Drug accountability**

The investigator or designee will receive the investigational drugs delivered by the sponsor when the following requirements are fulfilled:

- Approval of the clinical trial protocol by the IRB / ethics committee,
- Availability of a signed and dated clinical trial contract between the sponsor and the investigational site,
- Approval/notification of the regulatory authority, e.g. competent authority,
- Availability of the curriculum vitae of the Principal Investigator,
- Availability of a signed and dated clinical trial protocol,
- Availability of the proof of a medical license for the Principal Investigator,
- Availability of FDA Form 1572 (if applicable).

Investigational drugs are not allowed to be used outside the context of this protocol. They must not be forwarded to other investigators or clinics. Participants should be instructed to return used (empty blisters) partially-used and unused investigational drug.

The investigator or designee must maintain records of the product's delivery to the trial site, the inventory at the site, the use by each participant, and the return to the sponsor or warehouse / drug distribution centre or alternative disposal of unused products. If applicable, the sponsor or warehouse / drug distribution centre will maintain records of the disposal.

These records will include dates, quantities, batch / serial numbers, expiry ('use- by') dates, and the unique code numbers assigned to the investigational medicinal product and trial participants. The investigator or designee will maintain records that document adequately that the participants were provided the doses specified by the Clinical Trial Protocol (CTP) and reconcile all investigational medicinal products received from the sponsor. At the time of return to the sponsor or appointed CRO, the investigator or designee must verify that all unused or partially used drug supplies have been returned by the clinical trial participant and that no remaining supplies are in the investigator's possession.

## 4.2 OTHER TREATMENTS, EMERGENCY PROCEDURES, RESTRICTIONS

### 4.2.1 Other treatments and emergency procedures

Please refer to section [5.3.5.1](#) for handling participants with positive report of suicidal ideation and/or behavior.

### 4.2.2 Restrictions

#### 4.2.2.1 Restrictions regarding concomitant treatment

A list of restricted concomitant medications and drugs with potential pharmacokinetic interactions with the trial compound BI 1358894 can be found in the ISF. The list is not comprehensive. For example, drugs that are solely indicated for diseases that are excluded in this trial - like cancer drugs - may not be listed.

Use of ECT, TMS and Ketamine/S-Ketamine are restricted during the trial and would lead to study discontinuation (refer to section [3.3.4.1](#)).

Participants on statins should be monitored for statin-related toxicity including signs of myopathy, weakness, muscle pain, etc. along with clinical lab results. If statins are concomitantly used during the trial, the highest dose should not be taken together with the investigational compound. If participant in this trial is on the highest recommended statin dose, investigator should consider changing the statin dose to the next lower dose recommended for the respective statin if appropriate.

Please note:

- Investigators may use their clinical discretion to wash out (at least 3 half-lives of referenced medication) the restricted medications during the screening period. The participant must adhere to the screening visit dose of the background SSRI/SNRI/bupropion until the end of the trial or end of treatment.
- Participants, who, in addition to their monotherapy with an SSRI/SNRI/bupropion, are taking additional low dose antidepressant medications for purposes other than treating depressive symptoms, are not excluded. The dose must be less than the lowest dose indicated for MDD (see ISF for details).
- Participants who are on stable treatment with ongoing benzodiazepines and/or non-benzodiazepine hypnotics (refer to the ISF) for insomnia or anxiety for at least 28 days prior to screening should continue without change for the entire trial duration. For participants who are not on current treatment of insomnia and anxiety symptoms at the time of screening, the protocol will allow concomitant use of benzodiazepines or non-benzodiazepine hypnotics during the trial for up to 7 days at dose equivalent to  $\leq 1.0$  mg lorazepam per day, for management of AEs (e.g. anxiety and/or insomnia). Such drugs should be stopped after the AE is resolved, at the discretion of the Investigator. If longer

duration of treatment is needed, further re-evaluation is required by investigator for every 7 days per treatment cycle (and possibly more cycles if needed). Refer to ISF for dose equivalence information and comprehensive list of allowed concomitant medications.

- In case of AEs, any treatment deemed necessary per the clinical judgment of investigator for the management of AEs considering participant safety is allowed.

For further guidance investigators are referred to the actual Investigator's Brochure or may contact the sponsor.

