**Option 1:** An early EoT Visit must be conducted within 7 days of the last dose of trial medication for participants who agree to conduct regularly scheduled visits after premature drug discontinuation (if consistent with the planned visit schedule, the eEOT can replace the next regularly scheduled clinic visit). After this early EOT visit, participants should be followed up according to the regularly scheduled visit for both clinic and phone visits until Visit 8 and must complete the FUP Visit 28+2 days after the drug discontinuation date. All procedures should be completed, with the exception of trial drug procedures and [REDACTED]. If FUP visit (early drug discontinuation date + 28+2 days) can be completed prior to the date of the planned Visit 8, no additional FUP is needed. However, end of study participation must be completed.

**Option 2:** An early EoT Visit must be conducted within 7 days of the last dose of trial medication. If the participant is not willing to return for all regularly scheduled visits, at a minimum they must return for Visit 8 and FUP. If FUP visit (early drug discontinuation date + 28+2 days) can be completed prior to the date of the planned Visit 8, no additional FUP is needed. However, end of study participation must be completed.

1 Prior to any trial related procedure, may also be done at an extra visit up to 2 weeks before V1.

2 Urine drug screen at screening visit only. For WOCBP, a serum pregnancy will be performed at screening and a urine pregnancy tests at all clinic visits beginning with V2. If a urine pregnancy test is positive, a serum test needs to be performed for confirmation.

3 Participants will bring trial medication (used/unused blister and covering packages) to site visits for compliance check (V3/V4/V6/V8) and for resupply (V4 and V6). Participants have to take the morning dose of the IMP, at the trial site at all clinical visits, except EOT at Visit 8 also to allow [REDACTED]. Last regular intake of the trial drug is the day before EOT visit. Please refer to footnote 4.

[REDACTED]

[REDACTED]

[REDACTED]

7 After the EoStudy visit (= individual participant's end of the trial) the investigator should report only any cancers of new histology and exacerbations of existing cancer, trial treatment related SAEs and trial treatment related AESIs of which the investigator may become aware of and only via the BI SAE form, please see section [5.3.6.2.1](#).

8 Telephonic Visit

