| • Worsening of the depression
• Occurrence or increase of suicidality | Even though mitigation measures are applied, this cannot be completely ruled out | Participants will remain on their stable anti-depressive treatment with an SSRI/SNRI/bupropion and psychotherapy, where applicable. Placebo is adjunctive to this treatment. Frequency of clinic visits with suicidality assessments are optimized. Suicidal participants will be excluded from trial participation (refer to section 3.3.4.1) |
| Possible or known risks of clinical relevance for this trial      | Summary of data, rationale for the risk                                   | Mitigation strategy   |
| Quetiapine   |  |  |
|  |  | Management of symptoms, evaluation, and follow-up as needed to ensure participant safety, per investigators clinical judgment.   |

|   |  |  |
|---|--|--|
|   |  |  |
|   |  | Participants on these medications will be excluded from trial and use of these drugs will be restricted during the treatment period. If such medication is used during the trial for some reason, Investigator should stop either this medication or IMP per the clinical judgment.  |
| Possible or known risks of clinical relevance for this trial | Summary of data, rationale for the risk | Mitigation strategy   |
| quetiapine Placebo  |  |  |
|   |  | 

Participants will remain on their stable anti-depressive treatment with an SSRI/SNRI/bupropion and psychotherapy, where applicable. Placebo is adjunctive to this treatment.

Frequency of clinic visits with suicidality assessments are optimized.

Suicidal participants will be excluded from trial participation (refer to section 3.3.4.1)

 |

| General risk of psychoactive drugs  |  |  |
|---|--|--|
| Possible or known risks of clinical relevance for this trial                          | Summary of data, rationale for the risk  | Mitigation strategy  |
| Trial procedures  |  |  |

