#### 3.3.4.1 Discontinuation of trial treatment

An individual participant will discontinue trial treatment if:

- The participant wants to discontinue trial treatment, without the need to justify the decision.
- The participant has repeatedly shown to be non-compliant with important trial procedures and, in the opinion of both, the investigator and sponsor representative, is not willing or able to adhere to the trial requirements in the future.
- The participant needs to take concomitant medication that interferes with the investigational medicinal product or other trial treatment; refer to the ISF.
- The participant undergoes an ECT or TMS.
- Participant receives Ketamine /S-Ketamine treatment during the course of the trial.

Proprietary confidential information © 2023 Boehringer Ingelheim International GmbH or one or more of its affiliated companies

- The participant can no longer receive trial treatment for serious medical reasons (such as surgery, adverse events, other diseases, or pregnancy), per investigator's clinical judgement. In case of a temporary reason, trial treatment should be restarted if medically justified.
- Pregnancy occurs during the trial. (Once a participant has been enrolled in the clinical trial and has taken trial medication, the investigator must report any drug exposure during pregnancy which occurred in a female trial participant to the Sponsor immediately (within 24 hours) by means of Part A of the Pregnancy Monitoring Form to the Sponsor's unique entry point).
- The participant must discontinue treatment with trial medication if:
  - The participant develops suicidal ideation of type 4 or 5 in the C-SSRS (i.e., active suicidal thought with intent but without specific plan, active suicidal thought with plan and intent) or suicidal behaviour (i.e. actual attempt, interrupted attempt, aborted attempt or preparatory acts or behavior).
  - In the event of worsening of MDD which requires medical treatment which is on the list of restricted medications (refer to ISF), the trial drug has to be discontinued.

In addition to these criteria, the physician may discontinue treatment at any time based on his or her clinical judgment. For all participants the reason for withdrawal from trial treatment (e.g. AEs) must be recorded in the CRF. These data will be included in the trial database and reported.

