#### Participants prematurely discontinuing trial drug

Participants who discontinue trial drug prematurely should ideally be observed until trial end as if they were still receiving blinded trial treatment. If this is not possible, then participants should be encouraged to come back to the site and complete week 6 visit procedures, with the performance of the MADRS scale as a minimum requirement. See section [Flow Charts](#) and [3.3.4.](#) for further options.

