#### **Withdrawal of consent**

If a participant is not willing to continue in the trial until to the end of the trial, Visit 8 should be scheduled and completed instead of the next scheduled visit as soon as possible. Also the EoStudy visit should be performed to assess and monitor safety. If the participant refuses to participate at an EOT Visit and withdraws consent for any reason (without the need to justify the decision), the trial completion page of the eCRF has to be filled in. All unused trial medication will be collected and trial drug diary will be checked by the site. If participant discontinues prematurely for safety reasons or withdraws consent, trial medication administration and [REDACTED] will not be performed at EOT Visit (please refer to section [3.3.4.1.](#)).

It is important to distinguish between premature trial drug discontinuation, i.e. early discontinuation, and complete withdrawal of consent to participate in further trial procedures.

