#### **6.2.2 Follow-up period and trial completion**

For all participants who had at least one dose of trial medication, the follow-up visits will be performed as described in section [3.3.4.](#)

If the last day of trial drug intake is different from the day prior to the EOT visit, the date of the last day of trial drug intake will be used for calculation of the FUP visit dates.

Participants who finish the randomized treatment period according to the protocol, will return to the clinic for the end of study (EoStudy) Visit 9. Trial completion is defined as participants having reached the FUP visit within the specified window per the [Flow Chart 1](#). The trial completion page in the eCRF has to be entered.

For all randomized participants, termination of trial medication and trial completion must be recorded on the corresponding eCRFs.

Should it be not possible for the participant to attend a follow up visit at the trial site, a visit out of time window should be performed as soon as possible; if a visit at the site is not possible at all, at least a phone contact should occur at the scheduled follow-up visit time point.

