#### **7.4.3        Supplementary analysis**

An additional analysis of the primary endpoint will repeat the primary analysis methodology (MMRM/MCPMod) specified in [Section 7.4.1](#), but under a treatment policy estimand, i.e., effectiveness/intention to treat. This estimand approach will use all available MADRS data, including data collected after any intercurrent event listed in [Table 3](#). As discussed in [Section 6.3](#), an intercurrent event of death will be handled using a hypothetical approach.

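### Protocol 4.2.2.1 and 6.2.1 contradict 3.3.4 on what follows early stopping, so sites can lose Week 6 MADRS that the supplementary treatment-policy analysis needs

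*Protocol*

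**What the plan says.** Protocol 3.3.4.1 lists events after which an individual stops trial treatment. One entry is "The participant undergoes an ECT or TMS"; ketamine, C-SSRS type 4 or 5 ideation and suicidal behaviour are also listed. For people who stop drug early, 3.3.4 asks that they ideally be observed to the end of the trial, and otherwise be encouraged to attend Week 6 on its scheduled date. Option 2 in Flow Chart 1 is firmer: after an early EOT visit, "at a minimum they must return for Visit 8 and FUP". Section 6.2.1, on premature drug discontinuation, agrees: "participants should be encouraged to come back to the site and complete week 6 visit procedures", with MADRS as the minimum.

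Other passages read differently:

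- 4.2.2.1, citing 3.3.4.1: "Use of ECT, TMS and Ketamine/S-Ketamine are restricted during the trial and would lead to study discontinuation".
- Table 1.4.2:1, also citing 3.3.4.1: "Suicidal participants will be excluded from trial participation".
- 6.2.1, Withdrawal of consent, for someone unwilling to stay to the end: "Visit 8 should be scheduled and completed instead of the next scheduled visit as soon as possible".
- 6.2.2: "Trial completion is defined as participants having reached the FUP visit within the specified window".

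For the treatment-policy estimand, SAP 7.4.3 says: "This estimand approach will use all available MADRS data". This includes scores after any intercurrent event in SAP Table 3.

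**The concern.** Scores collected after an intercurrent event are what separate the treatment-policy analysis from the primary one. Protocol 7.2.2.1 and SAP 7.4.1 remove them from the primary analysis, and SAP 7.4.3 puts them back. If a site takes study discontinuation at face value, or uses up Visit 8 early, the participant has no Week 6 value.

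SAP 6.6 handles the gap through the MMRM under missing at random. The model in SAP 7.4.1 has no term for having stopped drug, so the missing Week 6 value is in effect predicted from similar participants in the same arm, most of them still on drug. The treatment-policy result then moves towards the hypothetical result it is meant to complement, and agreement between the two would be less informative than it looks.

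**Working it through.** No stated figure in the plan depends on this point, so there is none to reproduce. The check compares passages and counts days.

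**1. Passages side by side**

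| Situation | 3.3.4, 3.3.4.1, Options 1 and 2 | Conflicting or unclear passage |
|---|---|---|
| ECT, TMS or ketamine | Trial treatment stops; assessments continue, or at least Week 6 | 4.2.2.1: the study is discontinued |
| Suicidality on trial | Trial medication stops; same follow-up | Table 1.4.2:1: exclusion from participation (ambiguous) |
| Unwilling to continue all visits | Early EOT now, Visit 8 at Week 6 | 6.2.1: Visit 8 now |
| Early stopper reaching FUP | Visit 8 still due | 6.2.2: trial completion is reaching FUP |

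In the first row the citing section misstates the section it cites. The third row gives two different visits for the moment of stopping.

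**2. Where a brought-forward Visit 8 lands**

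In SAP Table 6 the Visit 8 window opens on Day 42. A MADRS on Day 20 falls in Visit 4 (Days 14 to 20). One on Days 21 to 27 or 35 to 41 falls in Visit 5 or 7, and the MMRM in SAP 7.4.1 models only Visits 3, 4, 6 and 8. In no case does a score before Day 42 supply a Week 6 value.

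**3. Can FUP come before Visit 8?**

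Let d be the day of last dose. FUP is due at d + 28 to d + 30. Visit 8 is planned for Day 43, with a window of Day 41 to 45.

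- Against Day 43: FUP can come first if d + 28 < 43, so d ≤ 14. It always does if d + 30 < 43, so d ≤ 12.
- Using the Visit 8 window: FUP can come first if d + 28 < 45, so d ≤ 16. It always does if d + 30 < 41, so d ≤ 10.

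Flow Chart 2 shows no MADRS at FUP. For these early stoppers, the 6.2.2 definition of completion can therefore be met before the Week 6 score is due.

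**4. Does SAP Table 6 keep a Week 6 score that is collected?**

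The Visit 8 window runs from Day 42 to d + 7, and the End of Trial window starts at d + 8.

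- The Visit 8 window is non-empty only if d + 7 ≥ 42, so d ≥ 35.
- It contains Day 43 only if d + 7 ≥ 43, so d ≥ 36.

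Read literally, a Day 43 MADRS from someone whose last dose was on or before Day 35 goes to End of Trial. The eEOT note says later scores are mapped to later visits by the windows above it. It does not say whether the d + 7 limit is lifted for the treatment-policy analysis.

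**5. Size**

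The visible text gives no rate of ECT, TMS or ketamine use, of suicidality or of early withdrawal. As assumptions only: if a share f of an arm loses Week 6 and their true scores differ from the model's prediction by g points, the arm mean shifts by f × g. For f from 1% to 10% and g from 5 to 15 points, this is 0.01 × 5 = 0.05 to 0.10 × 15 = 1.5 points. A treatment contrast moves only by the difference between the two arms' shifts. The direction is not given either, because a score after rescue treatment could be better or worse than predicted.

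**The case against.** The protocol has safeguards. Section 3.3.4 bars withdrawing anyone before discussion with the clinical trial leader, so a site should not close a participant on 4.2.2.1 alone. Section 3.3.4.2 has the investigator explain the options for continued follow-up. Both 4.2.2.1 and the risk table point to 3.3.4.1, which stops treatment only. These make loss less likely; they do not remove the contradiction.

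The risk-table line is weak evidence. It sits in a mitigation column and can be read as the entry exclusion for suicidality, although its cross-reference is to discontinuation on trial. It needs clarifying and does not carry the point.

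The Withdrawal of consent paragraph covers people unwilling to continue, and it ends by telling sites to distinguish them from people who only stop drug. For someone who is truly leaving, a prompt visit secures a last score. That stands. The conflict remains for those who decline the full schedule but might still attend Week 6, the group 3.3.4 and Option 2 address.

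A reader might infer that 6.2.2 ends participation and adverse-event collection before Visit 8. The documents do not support this. Section 6.2.2 defers to 3.3.4 for follow-up visits, the flow charts foresee FUP before Visit 8, and Flow Chart 1 schedules adverse-event collection at Visit 8. What is left is a definition that should be made explicit for very early stoppers.

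**Conclusion.** The point holds as a contradiction in wording with a limited statistical consequence. Section 4.2.2.1 disagrees with the section it cites, and 6.2.1 (Withdrawal of consent) disagrees with 3.3.4 and Option 2 on which visit is done at stopping. Week 6 MADRS after discontinuation can be lost, depending on which passage a site follows. It is not certain to be lost: 3.3.4 itself speaks of what is ideal and encouraged, and only the flow charts make Visit 8 mandatory.

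Only the supplementary treatment-policy analysis is exposed. The drift towards the hypothetical estimand assumes that lost participants differ from same-arm participants still on drug in ways the model does not capture. The size cannot be stated from the documents; the range in the working rests wholly on assumed inputs and shows scale only.

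A reader might infer that the plan systematically loses those with the worst course, or that the proof-of-concept result is biased. Neither follows. Unwillingness to continue is not the same as a poor course, no event rates are given, and the primary analysis censors these scores by design.

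**What to change.** 1. Reconcile 4.2.2.1 with 3.3.4, 3.3.4.1 and Options 1 and 2, so that the protocol states consistently whether ECT, TMS or ketamine ends trial treatment or trial participation. Clarify the suicidality line in Table 1.4.2:1 in the same way. The clinical criteria, and which rule is right, are for the sponsor.
2. Reconcile the Withdrawal of consent paragraph in 6.2.1 with 3.3.4 and Option 2, so that sites know whether the early EOT visit or Visit 8 is done at the time of stopping.
3. Make clear that the completion definition in 6.2.2 does not close a participant before a Visit 8 that is still due.
4. In SAP Table 6, check that the Visit 8 limit of treatment stop plus 7 days does not drop the Week 6 MADRS of early discontinuers from the treatment-policy analysis, and state the mapping used there. Without this, corrected protocol wording may not secure the data.

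The cost is protocol wording, a letter to sites and a clarification in the SAP. No visit is added, since Option 2 already requires Visit 8.
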